### **3.3.1 Overview of biopharmaceutics**

Klu et al. (2012) studied the effect of storage conditions and the drug matrix on the survival of the *L.rhamnosus* GG strain. *L. rhamnosus* GG cells in an amount of  $10^7$ CFU/g were inoculated on a layer of full- or reduced-fat peanut oil. Inoculated peanut oil was stored at 4, 25, and 37 °C for 48 weeks. Samples were collected periodically to count populations of *L.rhamnosus* GG. The results indicated that there was no significant reduction in the number of viable *L. rhamnosus* GG cells in preparations stored at 4°C. The survival rate of *L. rhamnosus* GG decreased with increasing temperature and storage time. The drug matrix had no significant effect on the survival of *L.rhamnosus* GG, except for storage conditions at 37 °C. Populations of *L. rhamnosus* GG were maintained at > 6 log in preparations stored at 4 °C for 48 weeks and at 25 °C for 23-27 weeks. At a storage temperature of 37 °C, populations of 6 log size were not preserved even for 6 weeks.

In a 6-month human study, Tannock et al. (2000) performed the repeated analysis of the concentration of viable *L.rhamnosus* HN001 cells in a lyophilized powder stored in a nitrogen atmosphere at room temperature. The powder contained  $5.3 \times 10^7$  CFU at the beginning of the study and maintained this concentration after 6 months of storage; other bacteria other than lactobacilli were absent, and the viability of lactobacilli did not change for 6 months. In a study of the stability of the *L. rhamnosus* HN001 strain in infant formula stored at 30 °C, a decrease in bacterial viability was determined at a rate of 0.4 log per year.

### **3.3.2 Overview of clinical and pharmacological research data**

#### ***3.3.2.1 Pharmacokinetic characteristics***

The pharmacokinetic characteristics of probiotics can be broadly divided into three main groups:

- survival in the gastric environment;
- ability to adhere to the intestinal wall (colonization);
- metabolic pathway of active ingredients.

The active ingredients of probiotics are not always well known, so most studies are aimed at assessing the survival of probiotics in the human gastrointestinal tract (Marteau and Vesa 1998).

One of the main conditions for assigning a bacterial strain to probiotics is its ability to survive in the gastrointestinal tract. The role of probiotic strain survival for its effectiveness is not absolute, since even inactivated and dead cells exhibit immunological and health-promoting effects (Linares et al. 2017, Zhang et al. 2005). Despite this, viability is still considered a prerequisite for optimal functioning of the probiotic strain (Lahtinen 2012).

Goldin et al. (1992) studied the *Lactobacillus rhamnosus* GG strain for survival in the human gastrointestinal tract. In this trial, 76 volunteers took the *Lactobacillus* GG strain as a frozen

concentrate or fermented preparation in milk or serum. The strain was isolated from feces of all volunteers who took fermented milk or serum, and 86% of volunteers who took the frozen concentrate, according to the results of inoculation on one sample of feces from the volunteer. The studied microorganism was also present in the feces of subjects taking ampicillin at the time of the study. After stopping the introduction of this microorganism with food, Lactobacillus GG was preserved in the feces of 87% of volunteers after four days and 33% of participants after seven days. Lactobacillus GG strain reduced the activity of fecal bacterial beta-glucuronidase by about 80% in volunteers who received this strain with food for four weeks. This indicates that the Lactobacillus GG strain survives in the human gastrointestinal tract and temporarily colonizes it, as well as the fact that it affects the metabolic activity of resident microflora.

Saxelin et al. (1995) studied discharge of the L.rhamnosus GG strain with feces after oral administration. Twenty healthy volunteers received the Lactobacillus GG strain as gelatin capsules for 7 days in daily doses of  $1.6 \times 10^8$  CFU and  $1.2 \times 10^{10}$  CFU. All volunteers in the high-dose group had a distinguishable amount of Lactobacillus GG in their feces during the trial period. The studied strain was detected in the feces of all volunteers 3 days after administration. The effect on the total number of lactobacilli in the feces was not determined.

Stool was sampled before L.rhamnosus GG administration and on days 3, 5 and 7. Fecal samples were immediately frozen and stored in the refrigerator at  $-45^\circ\text{C}$ . Samples were analyzed for the presence of Lactobacillus and Lactobacillus GG on cups with MRS agar at pH 6.2. The plates were incubated anaerobically for 3 days at  $37^\circ\text{C}$  and the total number of Lactobacillus and typical Lactobacillus GG colonies was evaluated.

Lactobacillus GG was detected in the feces of all 10 volunteers in the higher dose group ( $1.2 \times 10^{10}$  CFU) during the test period (table 2). A slight decrease in Lactobacillus GG was observed on the seventh day, but the change was not statistically significant. In the lower-dose group, Lactobacillus GG was registered in feces of only one volunteer at the end of the treatment period (table 2). The introduction of Lactobacillus GG did not appear to affect the total number of lactobacilli in the feces (see the table below). It is worth mentioning that none of the volunteers had typical Lactobacillus GG colonies or any morphologically similar colonies in the fecal samples prior to the test (day 0, table 2).

The number of lactobacilli in stool samples (in CFU/g of feces) in healthy volunteers after oral administration of Lactobacillus GG for 7 days at doses of  $1.6 \times 10^8$  CFU/day or  $1.2 \times 10^{10}$  CFU/day.

**Table 2.** The number of Lactobacillus GG and the total number of lactobacilli in fecal samples of 20 healthy volunteers received the Lactobacillus GG strain as gelatin capsules for 7 days in daily doses of  $1.6 \times 10^8$  CFU and  $1.2 \times 10^{10}$  CFU.

| Dose                 | The number of Lactobacillus GG and the total number of lactobacilli in stool samples |          |                   |                   |                   |                   |                   |                   |
|----------------------|--|----------|-------------------|-------------------|-------------------|-------------------|-------------------|-------------------|
| CFU/
day          | Day 0  |          | Day 3             |                   | Day 5             |                   | Day 7             |                   |
|                      | Lb   | Lb
GG | Lb                | Lb GG             | Lb                | Lb GG             | Lb                | Lb GG             |
| $1.6 \times 10^8$    | $1.5 \times 10^8$  | ND       | $1.7 \times 10^7$ | ND                | $2.8 \times 10^8$ | ND                | $8.0 \times 10^7$ | $10^3$            |
| $1.2 \times 10^{10}$ | $9.2 \times 10^7$  | ND       | $2.1 \times 10^8$ | $2.0 \times 10^6$ | $2.5 \times 10^8$ | $1.5 \times 10^6$ | $9.8 \times 10^7$ | $1.2 \times 10^5$ |

Note: Lb – Lactobacilli, ND – not detected.

The study showed that orally administered Lactobacillus GG in gelatin capsules can be detected in the feces of healthy human volunteers when taken at higher doses ( $1.2 \times 10^{10}$  CFU).

Hibberd et al. (2014) conducted a study of a drug containing Lactobacillus rhamnosus GG in elderly healthy volunteers.

Fifteen elderly volunteers aged 66-80 received Lactobacillus rhamnosus GG capsules containing  $1 \times 10^{10}$  CFU twice a day for 28 days, and were monitored for 56 days.

The main goal of this open-label clinical study was to evaluate the safety and tolerability of  $1 \times 10^{10}$  CFU of Lactobacillus rhamnosus GG taken orally twice a day in elderly volunteers for 28 days. The study also determined the concentration of Lactobacillus rhamnosus GG excreted in the feces by day 28 and 56 of the study.

Lactobacillus rhamnosus GG was found in the feces of 11 out of 15 (73%) volunteers at the end of the treatment period (study day 28), although the number of colonies in the feces varied significantly from  $1.4 \times 10^3$  to  $1.3 \times 10^8$ . None of the volunteers was found to have Lactobacillus rhamnosus GG in the feces at the beginning of the study or by day 56 of the study.

No serious adverse events were reported in healthy volunteers during the study. A total of 47 adverse events were reported in 15 volunteers (1 to 7 per volunteer), 39 (83%) of which were assessed as mild, and 40% were assessed as possibly related to the use of Lactobacillus rhamnosus GG. The most common adverse events were recorded from the gastrointestinal tract (bloating, gas, and nausea), 27 of which were assessed as mild adverse events, and 3 as moderate. In the first week of taking LGG, mild and passing gastrointestinal symptoms were recorded, which did not affect the daily activity of the volunteers. After the first week, most of the gastrointestinal symptoms appeared periodically during treatment and during the follow-up period with no identified Association with LGG.

All AEs registered in this study are described in detail in table 3.

**Table 3.** AE description in healthy volunteers after taking *Lactobacillus rhamnosus* GG capsules containing  $1 \times 10^{10}$  CFU twice a day for 28 days

| Study day  | 1–3    | 4–7   | 8–14   | 15–28  | 29–64  | All time |
|--|--------|-------|--------|--------|--------|----------|
| Symptoms   | N (%)  | N (%) | N (%)  | N (%)  | N (%)  | N (%)    |
| Expected AE  | 5 (11) | 4 (9) | 6 (13) | 7 (15) | 9 (19) | 31 (66)  |
| Gastrointestinal disorders  |        |       |        |        |        |          |
| Abdomen distention   | 0 (0)  | 1 (2) | 1 (2)  | 0 (0)  | 0 (0)  | 2 (4)    |
| Flatus   | 3 (6)  | 1 (2) | 2 (4)  | 2 (4)  | 2 (4)  | 10 (21)  |
| Borborygmus  | 1 (2)  | 0 (0) | 0 (0)  | 0 (0)  | 0 (0)  | 1 (2)    |
| Diarrhea   | 0 (0)  | 0 (0) | 1 (2)  | 1 (2)  | 1 (2)  | 3 (6)    |
| Abdominal spasms or pain   | 0 (0)  | 0 (0) | 0 (0)  | 1 (2)  | 0 (0)  | 1 (2)    |
| Nausea   | 1 (2)  | 0 (0) | 2 (4)  | 0 (0)  | 2 (4)  | 5 (11)   |
| Vomiting   | 0 (0)  | 0 (0) | 0 (0)  | 0 (0)  | 2 (4)  | 2 (4)    |
| Loss of appetite   | 0 (0)  | 0 (0) | 0 (0)  | 1 (2)  | 0 (0)  | 1 (2)    |
| Epigastric burning   | 0 (0)  | 1 (2) | 0 (0)  | 1 (2)  | 1 (2)  | 3 (6)    |
| Constipation   | 0 (0)  | 1 (2) | 0 (0)  | 1 (2)  | 0 (0)  | 2 (4)    |
| Others  |        |       |        |        |        |          |
| Rash   | 0 (0)  | 0 (0) | 0 (0)  | 0 (0)  | 1 (2)  | 1 (2)    |
| Unexpected AE  | 0 (0)  | 1 (2) | 1 (2)  | 2 (4)  | 2 (4)  | 6 (13)   |
| Actinic keratosis  | 0 (0)  | 0 (0) | 0 (0)  | 1 (2)  | 0 (0)  | 1 (2)    |
| Fever  | 0 (0)  | 0 (0) | 0 (0)  | 0 (0)  | 1 (2)  | 1 (2)    |
| Headache   | 0 (0)  | 0 (0) | 1 (2)  | 0 (0)  | 0 (0)  | 1 (2)    |
| Knee pain  | 0 (0)  | 1 (2) | 0 (0)  | 0 (0)  | 1 (2)  | 2 (4)    |
| Kidney stones  | 0 (0)  | 0 (0) | 0 (0)  | 1 (2)  | 0 (0)  | 1 (2)    |
|  |        |       |        | 28     | 56     | All time |
| Unexpected AE (based on the results of physical examination or laboratory tests) |        |       |        | 7 (15) | 3 (6)  | 10 (21)  |
| Vital signs   |        |       |        |        |        |          |
| High blood pressure  |        |       |        | 0 (0)  | 1 (2)  | 1 (2)    |
| Low blood pressure   |        |       |        | 1 (2)  | 0 (0)  | 1 (2)    |

| Laboratory parameters             |       |       |       |
|--|-------|-------|-------|
| Decrease in hemoglobin concentration     | 2 (4) | 0 (0) | 2 (4) |
| Increased white blood cell concentration | 0 (0) | 1 (2) | 1 (2) |
| Increased blood urea nitrogen            | 2 (4) | 1 (2) | 3 (6) |
| Decrease in glucose concentration        | 1 (2) | 0 (0) | 1 (2) |
| Increase of glucose concentration        | 1 (2) | 0 (0) | 1 (2) |

Ninety-four percent (116) of the symptoms were disappearing, lasted for a short time, and did not require additional therapy. The study showed that *Lactobacillus rhamnosus* GG is safe and well tolerated by healthy adult volunteers aged 65 and older.

Pitino et al. (2010) studied six strains of *Lactobacillus rhamnosus* for their ability to survive in the upper parts of the human gastrointestinal tract. MRS broth was used as a carrier, and survival was evaluated in vitro by gastric digestion separately and in combination with duodenal digestion. The results indicated a high survival rate of all studied strains during both gastric and duodenal digestion. In particular, a very high survival rate was determined for three strains, which was evidenced by the degree of extraction in the range from 117 to 276 %. In accordance with the data on survival, a high level of lactic acid production was determined for all strains, which confirms the preservation of their metabolic activity during digestion.

Jacobsen et al. (1999) conducted an in vitro study on 47 strains of lactobacilli and additionally studied 5 selected strains in vivo. Selected strains were studied for resistance to pH 2.5 and 0.3% bovine bile, adhesion to Caco-2 cells, and antimicrobial activity against pathogenic intestinal bacteria in model systems. For LGG, the high adhesion capacity was determined, as well as resistance to gastric acid and bile salts (simulated by a medium with a pH of 2.5 and 0.3 % bovine bile). Under these conditions, the bacteria survived, but lost the ability to replicate. LGG was one of the strains selected for in vivo testing. Twelve healthy volunteers took two doses daily of 10^10 lyophilized bacteria of the selected strains for 18 days, followed by a washout period of 17 days. Fecal samples were collected on days 0 and 18, as well as on days 5 and 11 of the washout period. Bacteria were re-isolated mainly during the administration period (day 18; 7 cases out of 12). On day 23, only 2 of 12 cases were re-isolated with the LGG strain. No bacteria were re-isolated on day 29. The LGG strain also inhibited a number of pathogenic bacteria and had minimal effect on the normal intestinal microflora.

According to the results obtained in this study, the bacteria of the LGG strain survive during passage through the gastrointestinal tract and can be re-isolated during the introduction period. However, there was no long-term colonization of any of the studied bacterial strains.

Dommels et al. (2009) conducted a double-blind randomized placebo-controlled interventional clinical trial to assess the survival of *Lactobacillus reuteri* DSM 17938 and *Lactobacillus rhamnosus* GG strains in the human gastrointestinal tract after daily use of low-fat probiotic spread using traditional cultivation methods as well as molecular methods. Forty-two healthy volunteers were randomly assigned to one of three treatment groups in which they received 20 g of placebo spread (n = 13), 20 g of spread with *L. reuteri* DSM 17938 at a target dose of  $10^9$  CFU (n = 13), and 20 g of spread with *L. rhamnosus* GG at a target dose of  $5 \times 10^9$  CFU (n = 16) daily for 3 weeks. Fecal samples were collected before and after the intervention period. After three weeks of daily use of the spread containing the strain *L. reuteri* DSM 17938 or *L. rhamnosus* GG, a significant increase in the degree of recovery of viable probiotic lactobacilli in stool samples relative to the baseline level was determined according to selective counting. No such increase was observed in the placebo group. The results obtained indicate the ability of the LGG strain to survive in the human gastrointestinal tract. The number of viable bacteria of the *L. rhamnosus* GG strain in fecal samples was at the level of  $6.6 \log_{10}$  CFU/g after 3 weeks of using the *L. rhamnosus* GG spread, which contained, on average, from  $3.3 \times 10^{10}$  to  $5.6 \times 10^{10}$  CFU of *L. rhamnosus* GG per 20 g of spread. These numbers are comparable to the results of the evaluation of the extraction degree of *L. rhamnosus* GG bacteria from feces after taking them with different foods, which were published earlier.

Saxelin et al. (1993) studied the concentration of *Lactobacillus* GG bacteria in human feces after the oral administration. In this study, 44 healthy volunteers received *Lactobacillus* GG bacteria for 7 days in the form of enteric-coated tablets at a daily dose of  $1 \times 10^9$ ,  $4 \times 10^9$ , and  $8 \times 10^9$  CFU, as well as fermented milk at a daily dose of  $2 \times 10^9$  and  $1.2 \times 10^{10}$  CFU. All volunteers were observed for the excretion of the studied strain with feces on the 3rd day of the test period. The average content of LGG bacteria in feces did not significantly differ between the groups receiving tablets. When using fermented milk, there was a clear statistically significant increase in the average content of *Lactobacillus* GG bacteria in the feces after taking a dose of  $1.2 \times 10^{10}$  CFU/day compared to a dose of  $2 \times 10^9$  CFU/day. According to the results obtained, fermented milk and tablets with an enteric coating are effective carriers for the *Lactobacillus* GG bacteria strain used as a probiotic.

Alander et al. (1999) studied colon biopsies to demonstrate the adhesion of lactobacilli of the GG strain to the human intestinal mucosa and the persistence of this connection after discontinuation of this probiotic. In this study, volunteers took 100 ml of a commercial drink based on whey with hydrolyzed lactose fermented with the GG strain twice a day for 12 days. The daily dose of GG strain bacteria was about  $6 \times 10^{10}$  CFU. After taking the GG strain bacteria, the volunteers were

divided into three groups: those who underwent a colonoscopy immediately after the 12-day intake period, 1 week after stopping taking it, and 2 weeks after stopping taking the probiotic, respectively. Patients collected stool samples, which were first stored in home freezers at -20 °C (for up to 3 weeks), and then in the laboratory at -20 °C before analysis. Biopsies of the descending colon were immediately placed in a thioglycolate medium and stored at 4 °C until analysis was performed (within one day). Confirmatory PCR analysis was also performed on *L. rhamnosus* isolates.

There was a high level of matching (88%) between the results of the PCR analysis and the screening analysis based on the assessment of colony morphology and the lactose fermentation test, which confirms the overall reliability of strain identification. The number of colonies of the GG strain decreased as a function of time after stopping the probiotic to be taken.

GG strain bacteria were found in biopsies and last stool samples of all volunteers in group A. In group B, colonies of the strain *L. rhamnosus* GG were found in seven of the eight biopsies. However, only two of the eight subjects had colonies of the GG strain at a discernible level in the last fecal samples. None of the seven subjects from group C had colonies of the GG strain in the last fecal samples. However, colonies of the GG strain were found in the biopsies of two of the seven volunteers. According to the results obtained, the bacteria of the strain *L. rhamnosus* GG are capable of adhesion to the colon mucosa in vivo, where they remain for a long period of time after stopping taking the GG strain bacteria.

Saxelin et al. (1991) conducted a dose-response study to determine fecal colonization by bacteria of the LGG strain. Forty healthy adult volunteers took LGG strain bacteria in the form of lyophilized powder once a day for 7 days in doses  $1,5 \times 10^6$ ,  $1,5 \times 10^7$ ,  $1,5 \times 10^8$ ,  $1,5 \times 10^9$ ,  $1,5 \times 10^{10}$  and  $1.1 \times 10^{11}$  CFU/day. Fecal samples collected on day 0 and on each day of the treatment period were analyzed for the total number of lactobacilli and LGG strain bacteria. Bacteria of the LGG strain were not detected in fecal samples before the probiotic period and were absent in the fecal samples of subjects from groups with dosages of  $10^6$ – $10^8$  during the probiotic period. Two of seven subjects from the group with a dosage of  $10^9$  during the tests was periodically observed the colonization of feces with bacteria of LGG strain on distinguishable level, and all subjects of the groups with doses of  $10^{10}$  and  $10^{11}$  were observed colonization of stool with these bacteria at the level of  $10^5$ – $10^7$  CFU/g. There was no influence of level of intake of the bacterial strain LGG on the total number of lactobacilli, as well as the dominance of strain LGG in the feces. No adverse effects were observed.

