### **Adverse Reactions**

Adverse reactions are extremely rare in use of probiotic products.

Mild gastrointestinal disorders such as nausea, abdominal cramping, flatulence or abdominal distension have been reported.

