There was a significant and continuous decrease in the level of vitamin B1 in blood plasma during the study, as well as a slight but relevant decrease in this vitamin in the urine. These changes were associated with a 25% decrease in the bioavailable vitamin B1 in the subjects' diet. The content of vitamins B2 and B6 in blood plasma and urine changed slightly throughout the study, namely, most of these values decreased, but did not go beyond the normal ranges. According to the authors' conclusion, the bacterial flora of the studied yogurt did not affect the content of vitamins B1, B2 and B6 in the human body. No adverse effects were reported.

Schultz et al. (2003) conducted a study of the immunomodulatory effects of LGG. Ten healthy adults (6 men and 4 women) aged 21 to 43 (average age 29.9) took a single dose of lyophilized LGG strain  $2 \times 10^9$  CFU in capsules daily for 35 days. Stool samples were collected 3 weeks before the start of the study, the day before the first dose, and the day after the last dose. Blood samples were also collected during the last two designated periods. As part of this study, the reaction of peripheral blood cells to "own" and "allogenic" fecal samples was evaluated, the content of microorganisms of the *Bacteroides fragilis*, *Escherichia coli* group, pro- and anti-inflammatory cytokines (IL-10, IL-4, IL-6, IFN- $\gamma$ , TNF- $\alpha$ ) in the culture's supravascular fluid was measured, as well as the activation of CD4 T-lymphocytes.

Lactobacilli not distinguishable from LGG were isolated from the feces of all subjects at the end of the administration period. Three subjects had mild bloating, but no other adverse effects. There was a slight modulation of the cellular immune response, which was manifested mainly by an increase in CD4 T-lymphocyte activity and a decrease in the secretion of cytokines such as TNF- $\alpha$  and IL-6.

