
Based on the evidence of medium quality, it was suggested that probiotics were effective in AAD preventing. The summary data indicate an exact probiotic effect (RR: 0.46; 95% CI: 0.35-0.61) corresponding to the value of NNT = 10. Among the various probiotics studied, the most appropriate is the strain *Lactobacillus rhamnosus* or *Saccharomyces boulardii* at a dose of 5 to 40 billion colony-forming units per day due to the modest size of the NNT and very low probable frequency of undesirable events.

Hojsak (2017) summarized the available data on probiotic use for clearly defined clinical indications of importance in paediatrics. Individual probiotic strains (*Lactobacillus rhamnosus* GG and *Saccharomyces boulardii*) are reported to have proven efficacy in treating acute gastroenteritis and preventing antibiotic-associated diarrhea. Moreover, the effectiveness of the LGG strain in preventing nosocomial diarrhea and respiratory tract infections in nursing homes has been confirmed. The author has concluded that probiotic strains have different efficacy depending on the clinical indication and therefore recommends the use of strains with proven efficacy and safety.

Thomas et al. (2001) studied the effectiveness of the LGG strain in preventing antibiotic-associated diarrhea in adults. In a prospective, double-blind, randomized, placebo-controlled trial, 302 hospitalized patients (143 males and 159 females, average age 55.8 years, range 18-90 years) undergoing intravenous or oral antibiotic therapy were randomized to placebo groups in a daily dose of  $2 \times 10^9$  CFU 2 times/day in capsule form or strain LGG for 14 days. The main outcome was the proportion of patients who had diarrhea within 21 days of recruitment, defined as the presence of watery or loose stool for two consecutive days or at three times the usual frequency for a particular patient. Patients were also asked to record unwanted effects such as nausea, abdominal cramping, flatus or tympanites.

Against the background of the LGG strain, the incidence of diarrhea did not change; diarrhea occurred in 29-30% of patients in the trial and control groups. The study group and placebo group did not differ in the number, type and severity of reported undesirable effects.

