#### 5. Gastrointestinal symptoms

Mark the occurrence of each of these symptoms during the day and rate the severity of symptoms on a 5-point verbal scale (0 to 4):

[figure not shown]
Nausea:  Yes  No

[figure not shown]
Vomiting:  Yes  No

[figure not shown]
Flatulence:  Yes  No

Abdominal pain:  Yes  No

Decreased appetite:  Yes  No

Comments \_\_\_\_\_ and  
complaints: \_\_\_\_\_

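### Abdominal bloating or distension is a listed reaction to the product, but it is not a named item in the daily diary, so the trial is less sensitive to it than to the reactions it prompts for

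*Protocol*

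**What the plan says.** **Known reactions.** The product information in Protocol 3.1.1 (Adverse Reactions) states: "Mild gastrointestinal disorders such as nausea, abdominal cramping, flatulence or abdominal distension have been reported". The safety overview in Protocol 3.3.5 names the same four.

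**Volunteer study at the same dose and frequency.** Protocol 3.3.2.1 describes an open-label study of 1 x 10^10 CFU twice daily for 28 days: "Fifteen elderly volunteers aged 66-80 received" the capsules. It reports "A total of 47 adverse events were reported in 15 volunteers (1 to 7 per volunteer", and adds: "The most common adverse events were recorded from the gastrointestinal tract (bloating, gas, and nausea". Of the gastrointestinal events, "27 of which were assessed as mild adverse events, and 3 as moderate".

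**Other studies the protocol describes.** In a small immunology study in healthy adults (3.3.2.3): "Three subjects had mild bloating, but no other adverse effects". In the hospital trial of prevention in adults (3.3.3.2), distension was recorded separately from gas: "Patients were also asked to record unwanted effects such as nausea, abdominal cramping, flatus or tympanites".

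**The diary.** Item 5 of the patient diary (Protocol 17.3, Appendix 3, Days 1 to 17) instructs: "Mark the occurrence of each of these symptoms during the day and rate the severity of symptoms on a 5-point verbal scale". Five lines follow: nausea, vomiting, flatulence, pain in the abdomen and reduced appetite. The diary also has free-text space for comments and complaints.

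**Use of the diary for safety.** Adverse event frequency from diary records is a stated safety parameter (Protocol 5.1.2 and 9.1; SAP 8.1). Protocol 10.1.4 item 4 compares diary complaints between groups.

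**The concern.** The diary is the only instrument that asks about symptoms every day and grades them. It prompts for three of the four reactions the product text lists and leaves out the fourth. A mild, transient symptom that is prompted daily will usually be recorded more completely than one the patient must write in or recall at a visit. If the final report says bloating was no more frequent on LRG-002 than on placebo, that statement will rest on a weaker record than the matching statement for flatulence or nausea. This matters because showing safety is part of the study goal (Synopsis) and the results are meant to support authorization (Protocol 3.1).

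**Working it through.** **1. Listed reactions against diary item 5**

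| Reaction in Protocol 3.1.1 | Line in diary item 5 |
|---|---|
| Nausea | Yes |
| Abdominal cramping | Yes, as abdominal pain |
| Flatulence | Yes |
| Abdominal distension | None |

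Three of four are prompted. Flatulence cannot be assumed to cover distension, because the product text and Table 3 list them separately.

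**2. Reproducing Table 3 (Protocol 3.3.2.1)**

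- Gastrointestinal rows: distension 2 + flatus 10 + borborygmus 1 + diarrhea 3 + spasm or pain 1 + nausea 5 + vomiting 2 + appetite loss 1 + epigastric burning 3 + constipation 2 = 30. The text gives 27 mild + 3 moderate = 30.
- All events: 30 + 1 rash = 31 expected; 31 + 6 unexpected + 10 from examination or laboratory = 47. The text gives 47.

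**3. How common distension was**

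- Whole period: 2/47 = 4.3% of all events and 2/30 = 6.7% of gastrointestinal events. Flatus is 10/47 = 21.3% and nausea 5/47 = 10.6%. Diarrhea and epigastric burning have 3 each. Distension ties with vomiting and constipation at 2.
- Days 1-14, this trial's treatment length: flatus 3 + 1 + 2 = 6; nausea 1 + 0 + 2 = 3; distension 0 + 1 + 1 = 2; borborygmus, diarrhea, epigastric burning and constipation 1 each. The total is 6 + 3 + 2 + 4 = 15, and distension is third.

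The prose ranking therefore fails over the whole period and holds on days 1-14, there on two events.

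**4. What one added line would cover**

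- Item 5 now: flatus 10 + nausea 5 + vomiting 2 + pain 1 + appetite 1 = 19 of 30 (63%).
- With a bloating line: 19 + 2 = 21 of 30 (70%).
- Counting diarrhea through the stool record: 19 + 3 = 22 of 30 (73%) now, and 24 of 30 (80%) with the line.

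**5. Other routes by which bloating could be recorded**

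- Interview about adverse events at each visit (Protocol 9.3.4) and a physician's survey of the patient (10.1.4).
- Complaints collection at Visits 1, 2 and 3 and at unscheduled visits (Table 6).
- Palpation, percussion and auscultation of the digestive system (5.2.3.2.2).
- The diary comment line, with investigator review and follow-up questions (5.1.2).

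None of these names bloating. The scheduled visits are on Day 1, Day 7 ± 2 and Day 15 ± 2, so they fall about a week apart.

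**6. Direction of the effect**

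Both blinded arms use the same diary. If a fraction c of true cases is recorded in each arm, the recorded rates are c·p_T and c·p_R. The ratio p_T/p_R is unchanged, while the number of recorded cases and the difference c(p_T − p_R) shrink. Sensitivity falls, but neither arm is favoured. The primary endpoint rests on the stool record, stool analysis and the investigator's classification, not on item 5.

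**The case against.** The strongest reply is that the plan does look for adverse events beyond the diary list. A reader might infer from item 5 that bloating is recorded only if a patient volunteers it. The routes in step 5 of the working show otherwise: patients are interviewed, surveyed and examined, and distension is a sign an abdominal examination can show. Protocol 10.1.4 also analyses treatment-related gastrointestinal events found by standardized MedDRA queries, which is not confined to the five prompted symptoms. This stands. What remains is that bloating is not asked about by name each day and gets no daily severity grade.

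A second reply is that the five symptoms are a secondary efficacy endpoint (Protocol 5.1.1.2; SAP 7.2) and were not designed as a checklist of reactions. That is fair, but the same diary also feeds a safety comparison.

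Third, the controlled evidence in the protocol gives little reason to expect an excess. The adult prevention trial found no difference in unwanted effects (3.3.3.2). The Crohn disease trial found none in distension (3.3.4.2). A trial in children with irritable bowel syndrome reported less distension on the strain (3.3.3.5). This lowers the stakes, but it does not make the record of a listed reaction any more complete.

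**Conclusion.** The point holds as a minor, inexpensive improvement. A reaction the protocol itself lists has no daily prompt, so the trial is less sensitive to it than to the three listed reactions that do. The size is small: one mild symptom, 2 of 30 gastrointestinal events in the volunteer study. Sample size, primary endpoint and planned analyses are unaffected. The conclusion assumes that general questioning about a week later records mild symptoms less completely than a daily prompt; the documents do not quantify this.

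Three stronger readings are not supported:

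- **That the volunteer study used this trial's regimen.** Dose and frequency match. Duration (28 against 14 days), age (66-80 against 18-65) and the lack of a control group do not.
- **That a loss of power can be calculated.** The 3 of 10 subjects with bloating in Protocol 3.3.2.3 took 2 x 10^9 CFU daily, a tenth of this trial's 2 x 1 x 10^10 = 2 x 10^10 CFU. Table 5 in 3.3.5 shows three distension cases against a study of 6 people, so the denominator is unclear. The documents give no placebo rate of bloating and no proportion of unprompted cases captured.
- **That the comparison is biased.** Solicitation is identical in both blinded arms.

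**What to change.** Add one line to item 5 on every diary page (Days 1-17): Abdominal bloating/distension, Yes/No, severity 0-4. Compare it by arm in the diary-based adverse event analysis (Protocol 10.1.4 item 4; SAP 8.1). State that it lies outside the efficacy symptom list in Protocol 5.1.1.2 and SAP 7.2, so that the secondary endpoint keeps its five symptoms.

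The cost is one more daily question for the patient, a diary reprint and one eCRF field.
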